### 8.4 Participants Trial Duration

On average patients wait 79 days to undergo surgical treatment (NHS Hospital Episode Statistics, Pre-COVID19). Therefore, incorporating 24 months follow up atop of the average 2-3 months lead time to surgery, participants will be within trial for approximately 27 months.

## 8.5 Trial Objectives

### 8.5.1 Primary objective

- To detect a mean difference of 1 point in the mJOA scale at 24 months post-surgery between the laminectomy alone group and the laminectomy and fusion group

### 8.5.2 Secondary objectives

- Compare the short-term clinical effectiveness of laminectomy and laminectomy and fusion at 12 months post-surgery
- Compare pain, quality of life, surgical complications, and radiological measures between the two groups
- Undertake a detailed economic analysis
- Undertake a predefined secondary analysis of:
  - Number of levels treated
  - Presence / Amount of movement pre-operatively (>1mm subluxation on flexion/extension X-Ray)
  - Presence of auto-fusion at 1 or more cervical level pre-operatively (radiological evidence of spontaneous fusion between two adjacent vertebrae)
  - Presence of Kyphosis (C2-C7 Cobb Angle <0°)
  - Presence of Cervical Ossification of Posterior Longitudinal Ligament
  - Previous Cervical Spine Surgery
  - Age
- Undertake a predefined subgroup analysis of
  - Participants satisfying the criteria of modified K Line Negative, on pre-operative imaging

## 8.6 Trial Outcome Measures

### 8.6.1 Primary outcome measure

The primary outcome measure for this trial is the modified Japanese Orthopaedic Association Score (mJOA).

This will be conducted by telephone, by a suitably trained professional, blinded to the participants allocation. Patients will be informed of this at screening assessment and in writing via the PIS.

The mJOA is an 18-point professional administered scale (0 worst to 18 best), which evaluates motor dysfunction in upper and lower extremities, loss of sensation and sphincter dysfunction. The mJOA is the international standard, and most validated measure for assessment of function in DCM.

Whilst laminectomy with fusion is hypothesized to improve both pain and neuromuscular function, a single validated endpoint for use in English speaking populations, encompassing assessment of both domains does not exist for DCM.

Pragmatically, the mJOA was therefore selected as the single primary end-point, on the basis:

- (1) The recovery priorities for patients are pain, hand and walking function

- (2) The mJOA is the international standard, and most validated measure for assessment of neuromuscular function in DCM. It has been the primary endpoint for most leading trials (AO Spine North America, AO Spine International, CSM Protect, CSM Surgery and RECEDE Myelopathy). It primarily evaluates motor dysfunction in upper and lower extremities but also altered sensation (including pain) to the hand(s) and sphincter dysfunction.
- (3) Pain is a complex experience, and a single pain outcome tool has not been specifically validated for use in DCM
- (4) The NIHR HTA (Funder) favoured a single primary end point (vs. co-primary end point)
- (5) Although traditionally a clinician administered score, a version has now been developed for use remotely, potentially more conducive to current NHS practice due to the COVID19 pandemic.

Together therefore the mJOA targets hand and walking function (2 of the 3 recover priorities for patients), with some reference to pain. Further it is the best validated disease score, with established MCID and precedent across a number of DCM clinical trials.

Further it has been validated for remote assessment, and is therefore suitable for centralised and blinded outcome assessment by telephone.

#### 8.6.2 Secondary outcome measures

The following outcomes will be measured after surgery:

- Length of Hospital Stay
- Length of Operation

The following outcomes will be measured at 6-, 12- and 24-months post-surgery:

- SF36v2 (Quality of life) Score
- EQ5D-5L
- Neck Disability Index (NDI)
- Brief Pain Inventory (BPI)
- Douleur Neuropathique 4(DN4)
- Michigan Body Map (Pain Location)
- Surgical Complications (Defined by Tetreault et al 2019)
- Other Adverse Events, including mortality
- Cervical X-Rays (Alignment [C2–7 lordosis, C2–7 Sagittal Vertical Axis and T1 slope], Fusion, Movement)

The following outcomes will be measured at 12 months:

- MRI Cervical Spine (Decompression, Cord Signal Intensity)

These outcomes have been selected to align with the newly completed Core Outcome Set for DCM, in the absence of defined core measurement set at the time of trial set-up.

Domain	Outcome	Polyfix Tools
Neuromuscular	Neck Mobility	NDI

	Finger Strength	mJOA	
	Grip Strength	mJOA	
	Finger/Hand Dexterity	mJOA	
	Arm Weakness	mJOA	
	Leg Weakness	mJOA	
	Balance	mJOA	
	Sensory Dysfunction	mJOA	
	Bladder Dysfunction	mJOA	
	Faecal Incontinence	SF36v2	
Life Impact	Falls	EQ5D-5L	
	Mobility	mJOA	
		EQ5D-5L	
		SF36v2	
	Dependence	EQ5D-5L	
	Fatigue	SF36v2	
EQ5D-5L			
Pain	Mental Health	SF36v2	
		SF36v2	
		Location	Michigan Body Map
		Intensity	BPI
		Perception	BPI / DN4
Radiology	Pain Control	BPI	
	Cord Compression	Post-Operative MRI	
		Cord Signal Change	Post-Operative MRI
		Alignment	Post-Operative Cervical X-Rays
	Adjacent Segment Disease	Post-Operative MRI	
Economic Impact	Employment Status	Healthcare Resource Use Questionnaire	
	Cost of Care	Length of Stay	
Length of Operation		Healthcare Resource Use Questionnaire	
			Healthcare Resource Use Questionnaire
Adverse Events	Death	Other Adverse Effects	
	Surgical complications	Surgical Complications 	

With the exception of radiological outcomes (X-Ray and MRI Imaging), and an assessment of adverse events, including surgical complications, participants will be followed up using electronic or postal questionnaires ± telephone consultation. If the time point after an assessment exceeds 8 weeks, and there is no response, then the patient will be deemed as lost to that follow up.

### 8.6.3 Exploratory outcome measure

Further, this trial will invite participants to undertake digital assessments of finger, arm and leg function (See Appendix 4).

## 9 Selection and withdrawal of participants

### 9.1 Inclusion Criteria

To be included in the trial the participant must:

- Have given written informed consent to participate
- Be able to read and understand English
- Be aged 18 years and over
- Have a diagnosis of DCM, based on established criteria (see table below)
- Be scheduled for posterior surgery, involving 2 or more consecutive laminae

MRI Indicators	Clinical Symptoms	Neurological Signs
Effacement of CSF and deformation of cord%	Numb Hands	Pyramidal Weakness
T1 signal change	Clumsy Hands	Hyperreflexia
T2 Signal change	Bilateral Arm Paraesthesia	Positive Hoffman Sign
Segmentation of T2 signal change	Gait impairment	Upping Plantar Response
Reduction in transverse area of cord%	L'Hermitte's Phenomenon	Atrophy of intrinsic hand muscles
	Weakness	Spasticity/Clonus
		Broad based, unstable gait
If a patient is unable to undergo MRI (e.g. for an incompatible implant), a CT Myelogram compatible features are marked %		

### 9.2 Exclusion Criteria

The presence of any of the following will preclude participant inclusion:

- Mild and non-progressive DCM (defined as stable mJOA score >16 at two consecutive time points)
- Presentation in the context of acute trauma (e.g. central cord syndrome or spinal cord injury)

### 9.3 Treatment Assignment and Randomisation Number

An online randomisation system will be used to assign participants in a 1:1 ratio to treatment with either laminectomy alone or laminectomy and fusion. Stratified blocked randomisation will be used stratifying by baseline mJOA (<12 vs >=12), age (<60 years vs >=60 years) and time to onset (>6 months vs <=6 months); random block size will be used.

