### 8.2 Number of Centres

This is a multi-centre study involving approximately 20-30 sites in the UK and 5-10 sites internationally. The internal pilot phase will take place across approximately 10 UK sites. We have estimated annual, per site recruitment at 4-8 patients.

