## 15 **Statistics**

### 15.1 **Statistical methods**

The primary objective will be evaluated using a two-sided t-test at a 5% significance level. The trial is powered to detect a 1-point difference in the mJOA scale between arms.

The ordering of subsequent endpoints for formal hypothesis testing will be:

1. BPI Pain
2. Neck Disability Index
3. PCS component of the SF-36
4. MCS component of the SF-36
5. mJOA (Upper Limb, Motor Score)
6. mJOA (Lower Limb, Motor Score)

A range of MCID for these endpoints have been proposed using a range of methods. As secondary endpoints the trial is not implicitly powered to detect a specific difference, and instead analysis will estimate the difference. However, in order to recognise what is considered meaningful in advance, the following MCID are agreed based on the available literature; BPI 20mm, NDI 8 points, SF36 PCS 5 points, MCS SF36 4 points, mJOA Subdomain scores 1 point.

A descriptive analysis of the following secondary outcome measures will be provided:

- SF36v2 (Quality of life) Score
- EQ5D-5L
- Neck Disability Index (NDI)
- Brief Pain Inventory (BPI)
- Douleur Neuropathique 4(DN4)
- Michigan Body Map (Pain Location)
- Complications (including surgical site infection, wound breakdown, instrument failure)
- Adverse Events

- Cervical X-Rays (Deformity, Fusion, Movement)
- Neurological examination
- Myelopathy.org Symptom Inventory

A predefined subgroup analysis of the following variables will take place:

- Number of levels treated
- Presence / Amount of movement pre-operatively (>1mm subluxation on flexion/extension X-Ray)
- Presence of auto-fusion at 1 or more cervical level pre-operatively (radiological evidence of spontaneous fusion between two adjacent vertebrae)
- Presence of Kyphosis (C2-C7 Cobb Angle <0°)
- Presence of Cervical Ossification of Posterior Longitudinal Ligament
- Previous Cervical Spine Surgery
- Age

The following baseline covariates, in addition to the baseline value of the endpoint, will be used to adjust all comparisons:

- Time to onset
- Smoking status (yes/no)
- Age
- Psychiatric comorbidities (yes/no)
- Impaired Gait (yes/no)

A detailed statistical analysis plan will be produced before the final data base lock.

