## **16 Data handling and record keeping**

### **16.1 CRF**

Electronic case report forms will be used to collect the data, with paper forms as back up. All data will be entered onto a secure electronic database. The database, which will be and GDPR compliant, will be secured by appropriate access control and password protection. All trial data in the CRF must be extracted from and be consistent with the relevant source documents. The CRFs must be completed by the investigator or designee in a timely manner. It remains the responsibility of the investigator for the timing, completeness and accuracy of the CRF pages. The CRF will be accessible to trial coordinators, data managers, the investigators, Clinical Trial Monitors, Auditors and Inspectors as required.

Data provided to the central coordinating team will be checked for errors, inconsistencies and omissions. If missing or questionable data are identified, the central coordinating team will request that the data be clarified.

Study participants will provide explicit consent to the use of identifiable data for the purposes of the conduct of the study (e.g. centralised follow-up). The POLYFIX DCM trial management team will hold patient identifiable data (PID) on all participants including name, date of birth, gender,

NHS number or equivalent, home address and postcode, telephone number and email address where applicable.

For the purposes of data analysis the patient identifying information will be replaced with unique patient specific trials study code to anonymise the data and also allow for central blinded follow up. Sites will keep all data collected from their patients with personal data (e.g. full name, DoB, address etc) as well as completed/signed consent forms in their Site Files. When they enter data collected on the CRF to send to us each patient will only be identified by their trial ID number and their DoB.

**To comply with data protection legislation, PID will not be transferred to the UK from international sites. For international sites, their centralised follow up will be coordinated by a single lead centre.**

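### Section 15.1 fixes the covariates for all comparisons without centre or follow-up hub; adding them is a cheap, small gain in precision, not the cure of a bias

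*Protocol*

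**What the plan says.** - **Sites.** Section 8.2 plans "approximately 20-30 sites in the UK and 5-10 sites internationally", which is 25 to 40 centres. It adds: "We have estimated annual, per site recruitment at 4-8 patients".
- **Randomisation.** Section 9.3 states: "Stratified blocked randomisation will be used stratifying by baseline mJOA (<12 vs >=12), age (<60 years vs >=60 years) and time to onset". Three two-level factors give eight strata. Neither centre nor country is among them.
- **Analysis.** Section 15.1 states: "The primary objective will be evaluated using a two-sided t-test at a 5% significance level". The same section then says: "The following baseline covariates, in addition to the baseline value of the endpoint, will be used to adjust all comparisons". The list that follows is time to onset, smoking, age, psychiatric comorbidity and impaired gait. Centre, country and follow-up hub are absent. Under a plain t-test they would be absent too.
- **Follow-up.** Section 16.1 does not allow identifiable data from international sites to come to the UK, and continues: "For international sites, their centralised follow up will be coordinated by a single lead centre". Sections 8.6.1 and 9.4 make the primary mJOA a central, blinded telephone assessment shared among more than one assessor.

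**The concern.** Outcomes may well differ between centres. Section 10.1 leaves the laminectomy tool, screw type and grafting to the surgeon. Section 10.2 recognises that surgeon experience might matter but handles it only through site and surgeon eligibility. Coordination of follow-up, possibly including who scores the primary outcome, also differs between UK and international participants.

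Centre and hub are known for everyone before randomisation, so using them needs no new data. With centre in neither the strata nor the adjustment list, two things follow. Between-centre variation stays in the residual of the primary and ordered secondary comparisons. Any chance imbalance of arms within centres, or between hubs, is not adjusted for. What is at stake is some precision.

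The point is not merely a detail for the statistical analysis plan, because section 15.1 already states an adjustment set and applies it to all comparisons.

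**Working it through.** **1. The protocol's own figure.** Inputs from section 15.3: difference 1 point, SD 2.89, two-sided 5% t-test, 90% power, 10% dropout. The t-test needs 176.5, so 177 per arm and 354 evaluable; 354/0.9 = 393.3, so 394. This reproduces exactly. The unadjusted SE is 2.89 × √(2/177) = 0.307, and power is 90.1%.

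**2. Centre size and balance.** 394/40 = 9.9 and 394/25 = 15.8, so about 10 to 16 participants per centre. With no balancing by centre, the chance of an 8:2 or worse split among 10 is 2 × P(X ≤ 2) = 10.9%. The chance of a 12:4 or worse split among 16 is 2 × P(X ≤ 4) = 7.7%. International sites are 5/35 = 14% to 10/30 = 33% of all sites.

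**3. Validity of the unadjusted test.** Simulating eight-stratum blocked allocation (assumed block sizes 4 and 6) over 25 or 40 centres, with ICC 0.01, 0.05 and 0.10 and 2,500 runs each, gave a type I error of 4.5% to 5.8%. There is no sign of inflation.

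**4. Gain from a centre random intercept.** The ICC is an assumption: 0.02, 0.05 or 0.10. Take 2.89 as the total SD, so σb² = ICC × 2.89² and σw² = (1 − ICC) × 2.89². For C equal centres with m = 354/C evaluable each and 1:1 allocation not balanced by centre, the information on the treatment effect is approximately

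I = (354/4) × [ ((m − 1)/m)/σw² + (1/m)/(σw² + mσb²) ], and SE = 1/√I.

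Example, ICC 0.05 and C = 25: m = 14.16, σw² = 7.934, σb² = 0.418, σw² + mσb² = 13.85. Then I = 88.5 × (0.1171 + 0.0051) = 10.82 and SE = 0.304.

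| Assumed ICC | SE, 25 centres | SE, 40 centres | Power by this formula |
|---|---|---|---|
| none removed | 0.307 | 0.307 | 90.1% |
| 0.02 | 0.307 | 0.307 | 90.2% |
| 0.05 | 0.304 | 0.305 | 90.5-90.7% |
| 0.10 | 0.298 | 0.300 | 91.4-91.7% |

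Generalised least squares with the variance components known gives about 90.2%, 90.5-90.8% and 91.5-91.9%. The two agree to about 0.2 points.

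**5. Two comparisons that bound this.** Multiplying the SD by √(1 − ICC) gives SE 0.304, 0.299 and 0.291 and power 90.6%, 91.5% and 92.8%. Those are ceilings, because they assume arms exactly balanced within centres, which this randomisation does not provide. Fixed centre dummies instead of a random intercept gave no gain in simulation (86-91% against 89-91% unadjusted).

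**6. Hub.** The documents give no hub difference. If the international share of participants equals its share of sites (an assumption), the between-arm difference in that share has a chance SD of √(0.14 × 0.86 × 2/177) = 0.04 to √(0.33 × 0.67 × 2/177) = 0.05. Even an assumed hub difference of a full mJOA point would typically move the treatment contrast by only 0.04 to 0.05 points, against an SE of 0.307.

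**The case against.** The strongest reply is that nothing is wrong. Allocation is individual and 1:1, centre and hub are crossed with arm, and chance imbalance over many small centres is already reflected in the unadjusted SE. Centre variance costs efficiency only, and for an ICC up to 0.05 the gain is less than one power point. The sample size also takes no credit for the baseline adjustment in section 15.1, so some precision is already in hand. A random intercept and a pooling rule could be left to the statistical analysis plan. Most of this stands, and it sets the low priority. The last part stands only partly, because section 15.1 already prescribes covariates for all comparisons, so that is the clean place to add these terms.

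A reader might infer three stronger things:

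- **That section 9.3 is defective.** Crossing centre with the eight strata would give 200 to 320 cells, or 394/200 = 2.0 down to 394/320 = 1.2 participants per cell. Leaving centre out of the blocks is defensible.
- **That the trial falls short of 90% power.** This would follow if 2.89 were a within-centre SD: unadjusted power would then be 89.7%, 88.7% or 87.0% at the three assumed ICCs. Section 15.3 does not say so. If the SD came from multicentre data, 394 already covers centre variance.
- **That the primary outcome is measured differently by arm.** Section 16.1 says only that follow-up is coordinated by a lead centre. Assessors are blinded, and more than one is used by design. That the hub lies outside the UK is an inference from the data-transfer rule. A scoring difference between hubs would fall on both arms alike.

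**Conclusion.** The point holds as a modest matter of efficiency. Section 15.1 omits two known, recorded factors from the adjustment it prescribes for all comparisons. There is no bias, type I error stays near 5%, and the unadjusted standard error is valid.

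Under the existing randomisation, a centre random intercept would add about 0.1 power points at an ICC of 0.02, 0.4 to 0.7 at 0.05 and 1.4 to 1.8 at 0.10. These figures rest on an assumed ICC, 354 evaluable participants, 2.89 as the total SD and known variance components, so they lean towards the favourable side. The benefit of a hub term cannot be sized from the documents, but chance imbalance should make it small. This is a cheap improvement of low priority.

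**What to change.** In section 15.1, add to the stated adjustment set:

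- centre as a random intercept;
- follow-up hub (UK central team or international lead centre) as a fixed effect.

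Apply both to the primary mJOA comparison and to the six ordered secondary endpoints (BPI pain, NDI, SF-36 PCS and MCS, and the upper- and lower-limb mJOA motor scores). Leave the randomisation in section 9.3 unchanged. Do not use fixed centre dummies, which brought no gain here.

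The cost is one sentence, one further variance component, one hub coefficient and a rule, set before database lock, for pooling very small centres. No new data are needed.

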### 9.4 Method of Blinding

Due to the nature of the trial, the clinical teams, patients and carers cannot be blinded to allocation. However, assessors of the primary endpoint (mJOA), can and will be blinded to participant allocation. This will be done centrally by a trained assessor. The same assessor will not be used for all cases.

## 9.5 Participant Withdrawal Criteria

Each patient has the right to withdraw from the trial at any time.

The investigator may discontinue a participant from the trial at any time if necessary and for reasons including the following:

- Significant non-compliance with treatment regimen or trial requirements
- An adverse event that requires discontinuation of treatment or results in inability to comply with trial procedure

Any data collected will remain in the trial and the patient will continue to be followed up unless consent is withdrawn. Patients who have been withdrawn from the trial will not be replaced as the power calculation for the trial allows for an 8% drop out rate.

All discontinuations and withdrawals will be documented in the CRF. If a patient wishes to discontinue, anonymised data collected up until that point will be included in the analysis.

## 10 Trial Treatments

The two surgical treatments to be compared in POLYFIX DCM are:

1. Laminectomy alone.
2. Laminectomy and fusion.

### 10.1 Treatment Summary

Both procedures are conducted under general anaesthesia, in the prone position. The head is typically supporting using a skull clamp (e.g. Mayfield™ or Sugita™).

Localisation of the spinal level to be operated on is usually based on anatomical markers. Intra-operative images may be obtained using fluoroscopy prior to ensure the correct levels are removed. This ensures the incision is correctly placed and not too long. Unless contraindicated, skin preparation should be with an alcoholic skin prep agent, care must be taken to avoid alcoholic skin preparations from running round into the eyes. Local anaesthetic with adrenaline is preferably used at the incision site.

#### 10.1.1 Intervention: Laminectomy and fusion

Whilst individual techniques may vary slightly, the principles of a cervical laminectomy are as follows:

- The patient is positioned prone, and the correct spinal level is identified
- A midline incision is made and dissection is undertaken down to the spinous process.
- A subperiosteal dissection to expose the spinous process, lamina and lateral masses of the desired levels is then performed.
- Fluoroscopy may be obtained to ensure the correct levels are removed.
- A posterior cervical laminectomy is performed using one of the following techniques:
  - A high-speed cutting burr
  - A manual laminectomy using a combination of rongeurs and instruments

- A footplate craniotome
- Instrumentation and fusion is performed.
  - Depending on the cervical level and surgeons' preference, either lateral mass screws or pedicle screws are inserted.
  - Appropriate length rods are then secured with set screws/caps.
  - Decortication is performed and bone graft material may be placed along the lateral mass edges bilaterally.
  - This can be supplemented or supported with synthetic products (E.g. Actifuse, Baxter)
- A subfascial drain can then be placed and the muscle, fascia and skin closed.

